8.9 Analysis Software

All analyses will be performed using SAS Software version 9.2 or higher.

9. STUDY SUBJECTS

9.1 Disposition of Subjects and Withdrawals

All subjects who provide informed consent will be accounted for in this study. The frequencies and percentages of subjects in each analysis set, study withdrawals, subgroups, and major protocol deviations will also be presented.

10. DEMOGRAPHICS AND OTHER BASELINE CHARACTERISTICS

10.1 Demographics

Age, height, weight, body mass index will be summarized by reporting the mean, standard deviation, median and range, and will be calculated by vaccine group and overall.

The frequencies and percentages of subjects by sex, country, age categories (for posting), ethnic origin, race, entry criteria fulfilled will be presented by vaccine group and overall. Demographic data will be tabulated for the All Enrolled, modified FAS and Safety sets.

10.2 Medical History

The frequencies and percentages of subjects with medical history will be presented by MedDRA system organ class and preferred term, by vaccine group and overall. Medical history data will be tabulated for the All Enrolled.

11. IMMUNOGENICITY ANALYSIS

11.1 Blood Samples

The frequencies and percentages of subjects with blood draws will be summarized overall and by vaccine group. Data will be tabulated for the enrolled set.

11.2 Primary Objectives Analysis

Not Applicable. The primary objective of the study is safety and all immunogenicity objectives are secondary objectives.

11.3 Secondary Objectives Analysis

Secondary Objective:

To evaluate the immunogenicity profile of two injections of *S. sonnei* 1790GAHB vaccine in healthy adults by measuring the anti-LPS *S. sonnei* serum IgG.

The measures of the immunogenicity outcome, (i.e., the anti-LPS *S. sonnei* serum IgG), will include:

- a. IgG geometric mean concentrations (GMCs) pre-vaccination (Day 1), 28 days after 1st vaccination and 28 days after 2nd vaccination, as determined by Enzyme-linked Immunosorbent Assay (ELISA), and applicable geometric mean ratios between post- and pre-vaccination samples.
- b. Number and percentage of subjects with seroresponse for anti- LPS *S. sonnei* at 28 days after 1st vaccination and 28 days after 2nd vaccination

Seroresponse is aimed to define a significant increase in post vaccination samples based on the biological performance of this specific serology assay and it is defined as:

- If the baseline value is greater than 50 ELISA Units (EU) then an increase of at least 50% in the post-vaccination sample as compared to baseline [i.e. $((\text{Post-vac} - \text{baseline})/\text{baseline})100\% \geq 50\%$]
- If the baseline value is less or equal to 50 EU then an increase of at least 25 EU in the post-vaccination sample as compared to baseline [i.e. $(\text{post-vac} - \text{baseline}) \geq 25 \text{ EU}$]
- c. Number and percentage of subjects with titers post vaccination concentration ≥ 121 for anti-LPS *S. sonnei* at 28 days after 1st vaccination and 28 days after 2nd vaccination
- d. IgG GMCs pre-vaccination (Day 1), 28 days after 1st vaccination and 28 days after 2nd vaccination by antibody titer at baseline (i.e., above vs. below the assay detection limit), as determined by ELISA, and applicable geometric mean ratios between post- and pre-vaccination samples.
- e. Number and percentage of subjects with seroresponse for anti- LPS *S. sonnei* at 28 days after 1st vaccination and 28 days after 2nd vaccination by antibody titer at baseline (i.e., above vs. below the assay detection limit)
 - A post vaccination concentration ≥ 121 anti-LPS serum IgG units in the GVGH ELISA corresponds to a titer of 1:800 in the ELISA method used by Cohen et al. (1989 J. Clin. Microbiol. 27:162). This antibody level is the median antibody concentration of a set of 87 convalescent subjects previously infected by *S. sonnei*. The value of 121 anti-LPS serum IgG units in the GVGH ELISA was determined by calibration against the Cohen ELISA (i.e., the GVGH standard serum was tested in Cohen's lab using the Cohen's methodology).

Statistical hypothesis:

This Phase 2a safety and immunogenicity trial is aimed to descriptively evaluate the safety and immunogenicity profiles of the study vaccines. No specific hypotheses are tested in this trial.

Statistical models:

GMCs

The ELISA concentrations will be logarithmically transformed (base10) (to fulfil the normal distribution assumption). For each treatment group, GMC will be calculated, with their associated two-sided 95% CIs, by exponentiating the corresponding log-transformed means and their 95% CI.

Additionally, within-subject GMRs will be computed for GMTs/GMCs at one month after first, and second vaccination versus baseline (day 1). The GMRs and 95% CIs will be constructed by exponentiating the mean within-subject differences in log-transformed titers and the corresponding 95% CIs.

Analysis of binary variables:

The number and percentages of subjects with seroresponse and with high seroresponse in ELISA concentrations from baseline, will be summarized. Two-sided 95% Clopper-Pearson CIs for the percentages will be computed.

Titers below the limit of detection will be set to half that limit for the purposes of analysis. Missing values of immunogenicity will be excluded from analyses (i.e. complete-case analysis) since they are considered missing completely at random, i.e. not informative and with no impact on inferences.

11.4 Exploratory Objectives Analysis

Explorative Objective:

There are no exploratory objectives in this trial.

12. EFFICACY ANALYSIS

12.1 Primary Objectives Analysis

Not Applicable.

12.2 Secondary Objectives Analysis

Not Applicable.

12.3 Exploratory Objectives Analysis

Not Applicable.

13. SAFETY ANALYSIS

The analysis of safety assessments in this study will include summaries of the following categories of safety data collected for each subject:

- Vaccine exposure.
- Solicited local and systemic adverse events and indicators of solicited adverse events.
- Unsolicited adverse events.
- Clinical Laboratory Investigations.

13.1 Analysis of Extent of Exposure

The frequencies and percentages of subjects with vaccinations will be summarized overall and by vaccine group. Data will be tabulated for the All Enrolled Set.

13.1.1 Safety Completeness Analysis

Solicited adverse events

The safety completeness analysis on solicited adverse events aims to identify subjects who completed diary cards, irrespective of severity will not be done for this Phase 2a study.

13.2 Solicited Local and Systemic Adverse Events

For details please refer to [section 6.5 of the protocol](#).

All solicited local and systemic adverse events will be analyzed. Implausible measurements will not be taken into consideration in the analysis but listed in the Appendix (see [section 6.3](#)).

Solicited adverse events will be reported at 30 minutes, 2 hours, 6 hours on day 1 and then daily until day 7 using structured diaries. The analyses of solicited adverse events will be done separately for the period 30 minutes – day 7. In addition solicited adverse events ongoing after day 7 will be presented as unsolicited AE.

For erythema and induration, recorded originally as diameters (mm), the following categorization will be used to summarize the data:

Type II: Grade 0 (< 25 mm), any (25-50 mm, 51-100 mm, >100 mm)

Body temperature will be broken down by route of measurement according to the recommendations of the Brighton collaboration and will be summarized according to the 3 schemes described below:

- by 0.5 °C increments: <36.0, 36.0 - 36.4, 36.5 - 36.9, 37.0 - 37.4, 37.5 - 37.9, 38.0 - 38.4, 38.5 - 38.9, 39.0 - 39.4, 39.5 - 39.9, ≥40.0°C
- by 1.0 °C increments: <36.0, ≥36.0-<37.0, ≥37.0-<38.0, ≥38.0-<39.0, ≥39.0-<40, ≥40°C
- <38.0, ≥38.0 °C

Fever, defined as a body temperature of ≥38°C irrespective of route of measurement, will be integrated to the summaries as a systemic adverse event.

The analyses will encompass summaries of the data on five levels:

1. Daily reports of subjects with solicited adverse events.
2. Time of first onset of solicited adverse events.
3. Solicited adverse events, maximum event severity by event and interval (30 min – day 7).
4. Duration of solicited adverse events, including ongoing AE after Day 7.
5. Solicited adverse events and indicators of solicited adverse events, occurrence of at least one event by category (local, systemic) and interval (30 min- Day 7).

For each of the time points or time intervals presented in the summaries, only subjects with at least one plausible observation (i.e., any non-missing values but excluding “Not done/unknown” and implausible values) for the solicited adverse events in the interval of interest will be considered. Subjects without plausible data (i.e. missing values or

reported as “Not done/unknown” and implausible values) will be removed from the denominator to prevent a downward bias (towards zero).

Level 1: Daily reports of solicited adverse event

For each of the time points only subjects with at least one plausible observation (i.e., any non-missing values but excluding “Not done/unknown” and implausible values) for the solicited adverse event in the interval of interest will be considered. Subjects without plausible data (i.e. missing values or reported as “Not done/unknown” and implausible values) will be removed from the denominator in order to prevent a downward bias (towards zero). Data collected will be summarized (frequencies and percentages of subjects) by vaccine group, solicited adverse event, vaccination number and time point.

Level 2: Time of first onset of solicited adverse events

The **time of first onset** is defined, for each subject, for each solicited adverse event, as the time point at which the respective solicited adverse event first occurred. For erythema and induration the following threshold(s) will be used ≥ 25 mm. The summary will provide the frequencies and percentages of subjects with first onset of each solicited adverse events by vaccine group and by each time point.

For each vaccination the first onset of the adverse event will be used for each subject. For any vaccination the worst adverse event across all vaccinations per time point will be used. Note, ‘not done’ is treated identical to ‘missing’.

Level 3: Solicited adverse events, maximum event severity by event and interval

The **maximum event severity** will be defined if there is at least one plausible non-missing observation (excluding “Not done/unknown” and implausible values) within this time interval. Each subject’s data will be aggregated across the time points of the interval and summarized according to the maximal severity observed for each adverse event, followed by a summary across subjects for each vaccine. Subjects without any solicited adverse events in the interval, i.e., missing values at each of the requested time points, will be removed from the denominator.

Level 4: Solicited adverse events, occurrence of at least one event by category (local, systemic) and interval.

The **occurrence of at least one solicited adverse event** is defined as “any” for a subject if he/she reports greater than “none” (≥ 25 mm for erythema and induration) for the respective event and “none” otherwise. The occurrence of at least one solicited adverse event (i.e., none versus any) will be summarized by category (i.e., local, systemic, any),

by vaccine group, by vaccination (after each vaccination and after any vaccination) and by time interval.

Medications to treat or prevent pain or fever will be summarized by frequencies and percentages of subjects reporting use of the medications by interval (30 minutes – day 7).

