Study Event	References								
Post Injection Assessment ^[f]	Sections 5.2.1 and 5.3.1 and 5.3.2		X	X	X	X	X	X	
Assess all AEs ^[g]	Section 7.1		X	X	X	X	X	X	X
Assess/ Inquire about AE leading to withdrawal, all SAE and AESI ^[h]	Sections 7.1.4.1 and 7.1.3		X	X	X	X	X	X	X
Assess Medications and Vaccinations	Sections 5.1.2 and 6.5	X	X	X	X	X	X	X	X
Study Termination	Section 5.5								X
Immunogenicity									
Serology blood draw	Sections 3.5 and 7.3		X			X			X

* Study days should be calculated based on the actual date of the previous visit (as to comply with requested Study Visit Time Window)

- Informed Consent to be obtained before any study procedure
- Physical examination must be performed by a qualified health professional in accordance with local regulations and licensing requirements designated within the Site Responsibility Delegation Log.
- Compliance with Exclusion/Inclusion criteria should be verified.
- In case of neutropenia, Complete Blood Count to be repeated on a weekly basis until resolution. If neutropenia occurs at the last study visit, Complete Blood Count to be repeated on a regular basis until resolution.
- A post-injection local and system adverse event and body temperature measurement will be performed approximately 30 and 60 minutes after each vaccination during the clinic visit.

- f. Beginning in the evening following study vaccine administration (approximately 6 hours), and daily thereafter through the following 6 days, solicited local and systemic adverse events including body temperature measurements and use of analgesics/antipyretics will be reported by field workers in a diary card based on subject's observation and interview.
- g. All unsolicited adverse events will be captured through 28 days following each vaccination.
- h. SAEs, AESI and AEs leading to study or vaccine withdrawal will be collected through entire study duration.

Table 3 Safety Tests Table

HEMATOLOGY
White Blood Cells (WBC)
Red Blood Cells (RBC)
Haemoglobin
Haematocrit
Platelets
Eosinophils
Basophils
Neutrophils
Monocytes
Lymphocytes
Prothrombin time*
CLINICAL CHEMISTRY
Total bilirubin
Aspartic Aminotransferase (ASAT/GOT)
Alanine Aminotransferase (ALAT/GPT)
γ-Glutamyl Transferase (γ-GT)
Lactic Dehydrogenase (LDH)
Alkaline Phosphatase (AP)
Total Proteins*
Glucose (random glucose)
Blood Urea Nitrogen (BUN)
Creatinine
Sodium
Potassium
SEROLOGY for VIROLOGY
HbsAg*
HIV antibodies*
PREGNANCY TEST
Human chorionic gonadotropin (hCG) in blood *

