3.4.2 Tools Used for Data Collection

Data will be recorded in a Subject Diary Card by appropriately trained study staff and entered on Case Report Forms (CRFs).

The subject Diary Card will be the only source document allowed for solicited local and systemic adverse events (including body temperature measurements), starting after the initial 60 minute post-vaccination period at the clinic. The following additional rules apply to documentation of safety information collected in the Diary Card.

The Investigator or delegated staff should monitor the Diary Card status throughout the study for compliance and any solicited local and systemic adverse events that were of concern to the subject.

1. No corrections or additions to the information recorded by the trained study staff within the Diary Card will be allowed after it is delivered to the site.
2. Any blank or illegible fields on the Diary Card must be described as missing in the CRF.

Case Report Forms

This study utilizes Case Report Forms (CRFs) to collect study-related data from each subject. A qualified site staff member(s) is required to enter subject data in the CRFs in English based on the medical information available in each subject's source record.

Data should be entered into the CRF in a timely fashion following each subject's clinic visit, study procedure, or home visit. Each subject's CRF casebook will be compared with the subject's source records by a GVGH-approved study monitor (or designee) over the duration of the study in order to ensure data collection accuracy.

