5.2.1 Post-vaccination Procedures

The following post-vaccination procedures will be performed on day 1 and day 29.

After vaccination, the subject will be observed for at least 1 hour including observation for unsolicited adverse events, solicited adverse events, and body temperature measurement. Record all safety data collected during this time in the subject's source document.

The site should schedule the next study activity (daily home visits) with the subject.

The subject should be reminded of the next planned study activity. The subject will be reminded to contact the site if there are any questions, and to contact the site immediately (or as soon as the subject is medically stable) if the subject has a medical condition that leads to a hospitalization or an emergency room visit or to a visit to/by a doctor or is of concern.

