5.3 Post-vaccination Visit(s)

5.3.1 Follow-up Home Visit(s)

Post-vaccination home visits will be performed daily by a field worker from day 1 (6 hours after vaccination) to day 7 to check solicited local and systemic adverse events and medications/vaccinations received, following discussion with the subject.

A Diary Card collected in person by study personnel will be used in this study to document solicited adverse events. The Diary Card is the only source for collection of these data; therefore, it is critical that the trained site staff completes the subject's Diary Card correctly. The appropriate site staff should be trained on how and when to complete each field of subject's Diary Card.

The appropriate site staff should be trained on how to measure local solicited adverse events and body temperature. The trained field workers who will perform the home visits will be instructed to direct the subject to the clinic if the event requires medical

supervision. The measurement of solicited local adverse events is to be performed using the ruler provided by the site.

The appropriate site staff should be instructed how to perform body temperature measurement using the thermometer provided by the site. The temperature recorded in the Diary Card will be the one measured by the site staff during point of contact with subject at home.

Appropriate training should be directed at the site staff who will perform the measurements of adverse events and who will enter the information into the subject's Diary Card. The identity of the person who will enter the information into the Diary Card must be documented in the subject's source record and in the study delegation log. Any individual that makes entries into the Diary Card must receive training on completion of the Diary Card. This training must be documented.

Whenever possible, the same individual should complete the subject's Diary Card throughout the course of the study.

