8.4.2.1.2 Analysis of Solicited Local, Systemic and Other Adverse Events

All solicited adverse events will be summarized according to defined severity grading scales.

Frequencies and percentages of subjects experiencing each adverse event will be presented for each symptom severity. Summary tables showing the occurrence of any local or systemic adverse event overall and at each time point will also be presented.

Post-vaccination solicited adverse events reported from day 1 to day 7 will be summarized for the intervals day 1-3, day 4-7, day 1-7 by maximal severity and by vaccine group. The severity of solicited local adverse events, including injection-site erythema and induration will be summarized according to categories based on linear measurement: 25 to 50 mm, 51 to 100 mm, >100mm.

Injection site pain and systemic adverse events (except fever) occurring up to 7 days after each vaccination will be summarized according to “mild”, “moderate” or “severe”.

Each solicited local and systemic adverse event will also be further summarized as “none” versus “any”.

Implausible measurements (for further definition see statistical analysis plan) will be left out of the analysis.

Use of antipyretics and analgesics will be summarized by frequency by type of use (prophylactic versus treatment) and percentage of subjects reporting use.

Body temperature will be summarized by 0.5 °C increments from 36.0 °C up to ≥ 40 °C and will be broken down according by route of measurement.

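### SAP 13.2 lists solicited-event time points that are not this trial's: a 2-hour assessment never made, no 60-minute one, all from diaries; it also omits two interval summaries the protocol requires

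*SAP*

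**What the plan says.** **Time points in the SAP analysis text.** SAP 13.2: "Solicited adverse events will be reported at 30 minutes, 2 hours, 6 hours on day 1 and then daily until day 7 using structured diaries". Several outputs in that section are built on these points: daily reports, time of first onset, maximum severity, and occurrence of any event.

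**Time points in the schedule.** Protocol Table 2, footnote e, says that a local and systemic assessment with "body temperature measurement will be performed approximately 30 and 60 minutes after each vaccination during the clinic visit". Footnote f continues: "Beginning in the evening following study vaccine administration (approximately 6 hours), and daily thereafter through the following 6 days". The SAP repeats both footnotes under its own Times and Events Table in section 3.

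**Data source.** Protocol 3.4.2 makes the Diary Card the only source for solicited events, but "starting after the initial 60 minute post-vaccination period at the clinic". For the first hour, protocol 5.2.1 says "Record all safety data collected during this time in the" subject's source document. Protocol 5.3.1, on home visits, says without any exception: "The Diary Card is the only source for collection of these data".

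**Intervals.** Protocol 8.4.2.1.2 requires solicited events to be "summarized for the intervals day 1-3, day 4-7, day 1-7 by maximal severity and by vaccine group". SAP 8.2.1 and 13.2 define one interval only, 30 minutes to day 7.

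**The concern.** The SAP contradicts both the protocol and its own schedule on when solicited events are assessed and where the data sit. These data feed primary safety endpoint (a), the number and percentage of subjects with solicited reactions in the 7 days after each vaccination.

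Two kinds of output are at stake. The by-time-point tables are laid out on the listed points, so an error in the list goes straight into them. The interval summaries depend on which records the programmer reads in. If only diary records or only the listed points are used, reactions seen in clinic could be left out.

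Separately, two interval tables that the protocol specifies for the primary objective do not appear in the SAP.

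**Working it through.** The plan gives no figure for this point, so the check sets the passages side by side.

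**Step 1. Compare the time points per vaccination.**

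| Time point | Protocol Table 2 and SAP section 3 footnotes | SAP 13.2 |
|---|---|---|
| 30 min | yes, clinic | yes, said to be from diaries |
| 60 min | yes, clinic | not listed |
| 2 h | not scheduled | yes, said to be from diaries |
| 6 h | yes, home visit | yes |
| Days 2 to 7 | yes, six daily visits | yes, six daily reports |
| Total | 3 + 6 = 9 | 3 + 6 = 9 |

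Eight points match. One listed point (2 h) is never collected, and one collected point (60 min) is not listed.

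**Step 2. Follow the list into the by-time-point tables (SAP 13.2, Levels 1 and 2).** Subjects without a plausible observation leave the denominator at each time point. At 2 h nobody has one, so the denominator is 0 in every group and the column is empty. First onset is the time point at which the event first occurred. A reaction first seen at 60 minutes and still present at 6 hours would be dated to 6 hours. One gone by 6 hours would have no place. Putting 60-minute findings in the 2-hour column would mislabel them.

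**Step 3. Follow the list into the interval summaries.** SAP 8.2.1 sets the solicited period as 30 minutes to day 7, and Table 7.7-1 names the solicited safety sets T30-D7. The day-1 assessments at 0.5, 1 and 6 hours all lie inside that period, so maximum severity and any versus none cover both clinic assessments by time. The weak points are the diary wording in 13.2 and Level 3, which aggregates over the interval's time points and refers to those requested. The only list of requested points is the one in 13.2.

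**Step 4. What one omitted subject would do.** Endpoint (a) changes only if a subject's sole positive finding from 30 minutes to day 7 comes from an assessment left out. The documents give no rate for this. As an assumed range with 24 per group: 0 such subjects, no change; 1 subject, 1/24 = 4.2 percentage points; 2 subjects, 2/24 = 8.3 points.

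**Step 5. Compare the intervals.** Protocol: day 1-3, day 4-7, day 1-7. SAP: 30 minutes to day 7, which corresponds to day 1-7. The other two are missing.

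**The case against.** The best defence is that endpoint (a) is a subject-level count over an interval. The SAP names 30 minutes as a time point, its interval contains 60 minutes, and no sentence excludes a 60-minute observation. Level 1 says that the data collected will be summarised, and the SAP's own schedule shows the 60-minute assessment as collected. The mock-ups, table of contents and program specifications, which are not among the documents, may map it correctly. The diary wording may simply be loose, and the ambiguity begins in the protocol, where 5.3.1 has no exception for the first hour. Nothing is tested, and Levels 1 and 2 still show early and late reactions by time point.

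Much of this stands. A reader might infer that clinic-observed reactions have no place in endpoint (a). The documents do not support that, for the reasons in steps 1 and 3. A reader might also count 72 x 2 = 144 sixty-minute assessments as lost. That is the number scheduled if everyone receives both doses, so at most a ceiling on readings without a listed time point. It is not a count of lost events.

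The defence does not cover the empty 2-hour column, the missing 60-minute slot or the two missing interval tables, which follow from the text as it stands. Time-point tables do not replace maximum severity within day 1-3 and day 4-7. Nor is it safe to rely on programmers to correct the list silently. For solicited events, SAP 13.2 points to protocol 6.5, which concerns concomitant medications. SAP 6.3 says subjects take some measurements directly, where protocol 5.3.1 has trained staff take them. SAP 8.8 refers to a specification folder for H03_01TP. These suggest text not fully adapted to this trial.

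**Conclusion.** The point holds for the schedule, the data source and the missing intervals.

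- **Certain if the SAP is followed as written:** an empty 2-hour column and no 60-minute slot in the daily and first-onset tables, and no day 1-3 or day 4-7 maximum-severity summaries.
- **Possible, not stated:** loss of clinic findings from maximum severity and any versus none, if programming reads only diary records or only the listed points. The effect on endpoint (a) cannot be estimated from the documents. Each affected subject would move a group percentage by 4.2 points with 24 in the denominator.
- **Not affected:** sample size, and any hypothesis test, since none is planned.

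This assumes that the schedule footnotes, which agree across both documents, describe what is done at the site. It also reads protocol 3.4.2 and 5.2.1 together as placing first-hour findings in the clinic source record. Protocol 5.3.1 can be read as limited to home visits, but it does not say so.

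**What to change.** In SAP 13.2, replace the time-point sentence with: 30 and 60 minutes after vaccination (clinic source record), about 6 hours on day 1, then daily to day 7 (Diary Card). Add a sentence saying that the clinic records enter time of first onset, maximum severity and any versus none. Restore the day 1-3, day 4-7 and day 1-7 summaries by maximum severity and vaccine group. Correct the cross-reference from protocol 6.5 to 7.1.1.

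In the protocol, reconcile 3.4.2 with 5.3.1 so that both name the same source for the first 60 minutes.

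The cost is a short SAP edit, a protocol clarification, time-point mapping in the programs and a few more tables or columns. No new data collection is needed. The change should be made before unblinding.
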